#### Trial Outcomes

| Trial Outcomes  | Explanation  |
|---|--|
| Primary outcome:
Hospital transfer due to infection, among hospital transfers | If the resident was transferred from the nursing home to a hospital, was the transfer made because the patient had an infection? |
| Secondary outcome:
Hospital transfer, among transfers                         | If the resident was transferred from the nursing home, were they transferred to a hospital?                                      |

Other outcomes are found in the below table. At the time of the study conception, these were planned for secondary manuscript submissions.

| Other Outcomes   | Explanation   |
|--|---|
| Multidrug-resistant organism (MDRO) colonization   | Was a resident colonized with a multidrug-resistant organisms (MDROs): (MRSA, VRE, ESBL, CRE)                               |
| Hospital transfer due to infection, among hospital transfers in Long Stay and Short Stay Subsets | As in above table, but with analyses stratified by length of stay.  |
| Hospital transfer, among transfers in Long Stay and Short Stay Subsets                           | As in above table, but with analyses stratified by length of stay.  |
| Emergency Department Transfer due to Infection; overall and in Long Stay and Short Stay Subsets  | Probability that a resident is sent to the emergency department for an infection, overall and stratified by length of stay. |

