## Statistical Analysis

Main trial results will be based on as-randomized, unadjusted analyses using generalized linear mixed models logistic regression. All outcomes will be assessed similarly. Here, we use the example of the primary outcome: transfer to a hospital for an infectious diagnosis. Clustering within nursing home will be accounted for using random effects, which are added model terms that allow unique baseline rates for each nursing home, and are used to account for clustered randomization. Model terms will include individual-level data on arm, nursing home, outcome events, trial period (baseline vs. intervention) and an interaction term between trial period and arm. Trial results will be assessed through the interaction term, which measures the difference in log odds between the baseline and intervention period between the two arms. We can write a simple version of the model symbolically as:

$$\text{logit}(\Pr[R_{ij}]) = \log\left(\frac{\Pr[R_{ij}]}{1 - \Pr[R_{ij}]}\right) = \beta_0 + \beta_1 \text{Arm}_{ij} + \beta_2 \text{Period}_{ij} + \beta_3 \text{Arm}_{ij} * \text{Period}_{ij} + b_i$$

where  $i$  is a nursing home,  $j$  is a resident within the nursing home, and  $R_{ij}=1$  if the transfer has an infection diagnosis and 0 if not.  $\text{Arm}$  and  $\text{Period}$  are indicator variables and are = 0 for patients in a nursing home in the control arm or baseline period and 1 if in the intervention arm or period, respectively. The random effect,  $b_i$ , allows for different readmission rates at each nursing home, and accounts for the clustering within a given nursing home. The ultimate effect of the intervention is assessed by  $\beta_3$ . If it is negative with p-value < .05 (or 95% CI excluding 0), then we can conclude that the intervention reduces the risk of infectious transfer.

Subsequent analyses will include as-treated and covariate-adjusted models. Adjusted models will account for individual age, gender, comorbidities (by diagnostic codes), and functional status scores. All analyses will use current versions of SAS (9.4), SAS/STAT (13.2, SAS Institute, Cary NC) and/or R (3.1.2).

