## Power

We assessed power via resampling methods. We used preliminary data on outcomes adjusted to an 18-month baseline and intervention period. First, each nursing home was randomly assigned to a study arm. Then, individuals were sampled with replacement from within each nursing home to simulate “baseline” period data. Individuals were sampled again to simulate the “follow-up” period data. For nursing homes assigned to intervention arm, observed readmissions among the sampled follow-up individuals were removed at a given probability to reflect the effect of the intervention. Finally, the analysis planned for the trial was conducted on the resampled “baseline” and “follow-up” data. In this case, the planned analysis is a generalized linear mixed model logistic regression with main effects for period and arm, with the study effect assessed via their interaction, as described above. To estimate power, we repeated this process 200 times. The proportion of times that the null hypothesis of no interaction effect was rejected, with alpha = .05, provided the estimated power. In contrast to analytic approaches to power, we also needed to find confidence limits on the estimate, which we did using exact methods. For cluster-randomized trials, this approach has the advantage that it does not require guessing the value of the intra-class correlation coefficient, or, importantly, its variability. In addition, this approach does not require an assumption of constant cluster size.

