For our primary outcome, preliminary data showed that 21.3% of hospital transfers from nursing homes were due to infection. For the probability of transfer due to infection, we assessed the power for a relative reduction of 15%, from 21.3% to 18.1%. Power was estimated at 89% (95% CI [83%, 93%]). For our key secondary outcome of the probability of transfer to a hospital among discharges, our preliminary data showed that 37.8% of discharges were associated with admission to hospitals across the nursing homes. For this outcome, we estimated the power for a relative reduction of 8%, from 37.8% to 34.8%, to be 99.5% (95% CI [97%, 99.9%]). Even at a relative reduction of 5%, we have 74% power (95% CI [67%, 80%]). These effect sizes are meaningful because there is tremendous national interest in reducing preventable readmissions, of which infections are a major cause. Reductions in overall readmissions of 1-3% are lauded as sizeable in the CMS Hospital Readmissions Program which fined 2,225 hospitals in its first year, with each fraction of a percent resulting in substantial lost revenue. The second year of this program saw a reduction of 0.6% in all cause readmissions. In summary, our power assessment demonstrates adequate power to detect plausible and meaningful effects of the proposed trial.

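### Does the power section overstate power by treating falls in a share as if they were falls in the number of transfers?

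*Combined protocol and SAP*

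**What the plan says.** In the final statistical plan (8/10/2019), the Trial Outcomes table defines the primary outcome as "Hospital transfer due to infection, among hospital transfers". The secondary outcome asks: "If the resident was transferred from the nursing home, were they transferred to a hospital". Under Statistical Analysis, the response for the primary model is 1 "if the transfer has an infection diagnosis and 0 if not", and the test is the arm-by-period interaction in a logistic mixed model.

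The Power section describes a resampling exercise with 200 repetitions in which "observed readmissions among the sampled follow-up individuals were removed at a given probability to reflect the effect of the intervention". It does not give the removal probability, or say whether a removed event stayed in the data as a non-event. The results are:

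- Primary: "we assessed the power for a relative reduction of 15%, from 21.3% to 18.1" per cent, with power 89% (interval 83% to 93%).
- Secondary: "we estimated the power for a relative reduction of 8%, from 37.8% to 34.8%, to be 99.5" per cent (interval 97% to 99.9%).
- Secondary, smaller effect: "Even at a relative reduction of 5%, we have 74% power" (interval 67% to 80%).

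The section supports these effect sizes by pointing to the national interest in avoiding readmissions, and it ends by concluding that "our power assessment demonstrates adequate power to detect plausible and meaningful effects of the proposed trial". The Power section of the original plan (2/4/2015) reads the same way.

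**The concern.** The aim, the simulation and the justification are all expressed in events: the Group 1 training module lists fewer infection-related transfers as a goal, the simulation removes readmissions, and the effect sizes are defended as reductions in readmissions. The quantity powered is a share, and the two scales differ because each denominator includes the events to be prevented.

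The targets 18.1% and 34.8% equal the baseline shares times 0.85 and 0.92. They match 15% and 8% fewer events only if each prevented event stays in the denominator as a non-event. For the primary outcome, that would turn a prevented infectious transfer into a non-infectious hospital transfer. If prevented events simply disappear, the same percentage cut in events moves the share less, and power is lower. A reader who took 15% as the cut in infectious transfers would put the chance of missing it at 11% when it could be about 28%. For an 8% cut in hospital transfers, the chance of a miss would be about a quarter instead of 0.5%.

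**Working it through.** **Inputs.** From the Power section: baseline shares 21.3% and 37.8%; target shares 18.1% and 34.8%; a further 5% scenario; power 89%, 99.5% and 74%; 200 repetitions; alpha 0.05. The documents give no counts of transfers or discharges, so power cannot be derived from first principles and has to be back-solved.

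**1. The plan's own figures.**
- Targets: 0.213 × 0.85 = 0.181; 0.378 × 0.92 = 0.348; 0.378 × 0.95 = 0.359. The first two match the printed values; the third is not printed.
- Exact 95% intervals on 200 repetitions: 178/200 gives 83.8% to 93.0%, 199/200 gives 97.2% to 99.99%, and 148/200 gives 67.3% to 79.9%. These agree with the plan apart from rounding.
- Internal consistency: calibrating on 74% at 35.9% predicts 98.7% at 34.8%, inside the stated 97% to 99.9%.

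**2. Share if a fraction x of events is prevented and nothing else changes.** The new share is p(1 − x)/(1 − px); equivalently, the odds are multiplied by (1 − x).
- Primary, x = 15%: 0.18105/0.96805 = 0.187, a relative fall of 12.2%.
- Secondary, x = 8%: 0.34776/0.96976 = 0.3586, a relative fall of 5.1%. The plan's 5% scenario is 0.3591.
- Secondary, x = 5%: 0.3591/0.9811 = 0.366, a relative fall of 3.2%.

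**3. The reverse conversion, x = 1 − odds(target)/odds(baseline).** Reaching 18.1% takes about 18.3% fewer infectious transfers. Reaching 34.8% takes about 12.2% fewer hospital transfers, and reaching 35.9% about 7.8% fewer.

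**4. Back-solved power, primary.** The log-odds difference between 21.3% and 18.1% is 0.2027. With 89% power the standard error is 0.2027/(1.960 + 1.2265) = 0.0636. At 18.7% the difference is −ln(0.85) = 0.1625, so power is Φ(0.1625/0.0636 − 1.960) = Φ(0.594), about 72%. The stated interval of 83% to 93% translates to 65% to 79%.

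**5. Back-solved power, secondary.** The 74% scenario gives a standard error of 0.0812/2.603 = 0.0312. At 35.86% the difference is −ln(0.92) = 0.0834, so power is Φ(0.0834/0.0312 − 1.960), about 76%. Calibrating on 99.5% instead gives about 82%. A 5% cut in events gives about 38%.

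**6. Partial replacement (an assumption; the documents give no figure).** If half of the prevented infectious transfers are replaced by a non-infectious hospital transfer, the primary share is 0.18105/(1 − 0.213 × 0.075) = 18.4% and power about 82%. If all are, it is 18.1% and 89%. If half of the residents spared a hospital transfer later leave for somewhere else, the secondary share is 0.34776/(1 − 0.378 × 0.04) = 35.3% and power about 93%.

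**7. Simulation of the contrast.** This used 28 homes, 2,000 runs, an assumed between-home SD of 0.3 on the logit scale, home fitted as a fixed effect, and sizes tuned to the stated power. The primary gave 89% with removed events kept in the denominator and 72% with them dropped. The secondary at 8% gave 99% and 75%. Because of the tuning, this confirms only the contrast, not the absolute level.

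**The case for a change.** The best case for acting is that a share reduction is not what a nursing home or payer cares about, and the plan justifies its effects in the language of readmissions. For the primary outcome, the assumption that prevented transfers vanish is the natural one, since stopping an infectious transfer does not create a different hospital transfer. The match between an 8% cut in hospital transfers and the plan's own 74% scenario needs no modelling. Stating how removed events were handled and adding the event equivalents would be cheap.

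The algebra stands, as does the observation that the section does not say how removed events were treated. What does not stand is the step to a misstated power. The plan nowhere calls its effect a 15% cut in the number of infectious transfers: it names the share, gives both endpoints and tests that share. The simulation text removes readmissions from sampled individuals, not the individuals themselves, which fits keeping the record with a changed outcome and yields exactly the printed targets. If records were dropped instead, about 18.3% of events had to be removed to reach 18.1%, and the reported power for that share still holds.

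On the secondary outcome, the no-replacement case is the extreme. A resident spared a hospital transfer may well leave later for another destination and so remain in the denominator.

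**Conclusion.** No change is needed. The stated power figures are not shown to be wrong for the shares they refer to, and they agree with one another. The lower figures are conditional: about 72% (65% to 79%) for the primary and about 74% to 82% for the secondary if no prevented transfer is replaced, rising to 82% and 93% if half are, and to the stated 89% and 99.5% if all are. They rest on a standard error back-solved from the plan's own power. Calling them inadequate also needs a threshold such as 80%, which the plan does not set; it offers its own 74% as supportive.

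The missing detail is one an analyst can fill. With other transfers unchanged, prevention multiplies the odds by one minus the fraction prevented, so an odds ratio for the interaction converts directly into a percentage of transfers prevented. A null result would be judged by the confidence interval for that interaction, not by planning power. The final plan postdates the end of the intervention period in December 2018, so a rerun could not alter the number of homes, and it would leave the model, outcome and success rule as they are. A sentence on how removed events were handled would be a courtesy to readers, not a correction.

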## The Protect Nursing Home Trial

### Statistical Plan Amendments

| Date      | Statistical Plan Amendments  |
|-----------|--|
| 2/4/2015  | Original   |
| 8/20/2018 | 

Defined 'other' outcomes for secondary publications. Previously, clinicaltrials.gov listed both secondary outcomes for the primary manuscript and outcomes for secondary manuscripts under the same heading. After the ability to separate the two under "other outcomes," we clarified additional outcomes that were not trial outcomes.

Multidrug-resistant organism (MDRO) colonization (separate aim from the trial in original grant; distinct design, methods, collection, analysis)

Hospital transfer due to infection, in Long Stay and Short Stay Subsets

Hospital transfer for any reason, in Long Stay and Short Stay Subsets

Emergency Department visits due to Infection; overall and in Long Stay and Short Stay Subsets

  |
| 6/19/2019 | 

Removed secondary outcome (antibiotic usage)

We had proposed to use the CMS Minimum Data Set (MDS) to assess this and other trial outcomes. At the time of the grant proposal, antibiotic usage was a newly-added variable. We assumed that this variable would increase in usage and accuracy with time. However, even five years after the variable was added, expert opinion from the creators of the MDS dataset, was that antibiotic data capture in MDS was poor and insufficient for analysis. Thus, the steering committee removed this as an outcome and filed a change with clinicaltrials.gov at that time. We note that MDS data is released 18 months following completion of a calendar year. This decision was made prior to receipt of any intervention data (2017-2018 MDS data) for the trial and prior to any data cleaning or analysis.

 |
| 8/10/2019 | 

Updated layout, no change in content or meaning

Removed randomization details from statistical plan

  |
